9. DISPOSITION AND WITHDRAWALS

All subjects who provide informed consent will be summarized.

Disposition summary will be provided by study period separately for all randomized subjects.

The frequency and percentage of randomized subjects who complete the study or discontinue early will be summarized by treatment group and overall. Reasons for discontinuation from the study will also be summarized.

The number of subjects in each population will be presented by treatment groups and overall.

A list of critical protocol deviations will be provided for the randomized population. A summary of critical or major protocol deviations with reason for the deviation will be provided as counts and percentages.

10. DEMOGRAPHIC AND OTHER BASELINE CHARACTERISTICS

Demographic data and other baseline characteristics will be presented and summarized for all randomized subjects.

No statistical testing will be carried out for any demographic or baseline characteristics. Patient characteristics will be recorded at the screening visit and will be listed by patients and summarized by treatment groups. Overall summaries will include descriptive statistics for continuous measures (n, mean, SD, median, minimum, and maximum) and for categorical measures (n, count, and percent). Missing categories will be represented as appropriate.

Rett syndrome history will be summarized by treatment and overall for the following:

- Duration of Rett syndrome (in months) defined as:

(Date of Informed Consent – Date of Diagnosis of Rett syndrome)/30.25

- Count and percentages of all responses for “Respiratory abnormalities”

11. MEDICAL HISTORY

Medical History information will be presented and summarized for the safety population and coded using Medical Dictionary for Regulatory Activities (MedDRA) dictionary Version 22.0.

Medical History will be recorded at the Screening visit.

Document:	\\ieedc-vnasc01\BIOSdata\Newron\Sarizotan\PXA76395\Biostatistics\Documentation\SAP		
Author:	[name]	Version Number:	V2
		Version Date:	[30March2020]
Template No:	CS_TP_BS016 – Revision 4	Reference:	CS_WI_BS005
Effective Date:	01Apr2016		

Counts and percentages of Medical History conditions will be presented by treatment groups, SOC and preferred term. Also a list of medical history findings will be provided.

12. MEDICATIONS

Medications will be presented and summarized for the safety population and coded using World Health Organization (WHO) DRUG dictionary of medical code.

Prior and concomitant medications during the study will be summarized using ATC level 3 coding.

- ‘Prior’ medications are medications which started and stopped prior to first dose of study medication.
- ‘Concomitant’ medications are medications which ended on or after first dose of randomized study medication or ongoing at the end of the study.

The number of patients with concomitant medications will be summarized using count and percentages by therapeutic class, preferred term, treatment group and overall. Patients are counted only once in each therapeutic class category, and only once in each preferred term category.

A list of prior and concomitant medications (includes procedures) will be provided separately.

Concomitant medication (includes procedures) summary will be provided period-wise separately.

See Appendix 1 for handling of partial dates for medications, in the case where it is not possible to define a medication as prior or concomitant, the medication will be classified by the worst case; i.e. concomitant.

13. STUDY MEDICATION EXPOSURE

Exposure to study medication in days will be summarized for the Safety Population.

The total duration of study medication administration will be taken from the “Study medication administration” form of the eCRF.

Duration of exposure (in Days) will be summarized descriptively.

Duration of exposure (in Days) = Date of Last dose – Date of First Dose +1

Interruptions and compliance are not taken into account for duration of exposure.

Document:	\\ieedc-vnasc01\BIOSdata\Newron\Sarizotan\PXA76395\Biostatistics\Documentation\SAP		
Author:	[name]	Version Number:	V2
		Version Date:	[30March2020]

Template No: CS_TP_BS016 – Revision 4
 Effective Date: 01Apr2016

Reference: CS_WI_BS005

14. STUDY TREATMENT NON-COMPLIANCE

List of the treatment non-compliance (<80%) will be provided for the Safety population based on the data from DB period.

15. EFFICACY OUTCOMES

Summaries will include descriptive statistics for continuous measures (n, mean, SD, median, minimum and maximum) and for categorical measures (n, frequency and percentage).

15.1. PRIMARY EFFICACY

15.1.1 PRIMARY EFFICACY VARIABLE & DERIVATION

The primary efficacy outcome in the double-blind period will be the percent reduction (change) from baseline in the number of apnea episodes (each ≥ 10 seconds in duration) per hour, during awake time. The data was obtained from the vendor Vivonoetics. Assessment of the respiratory outcomes was performed at home on any 3 days in each of the first 3 weeks of the screening period, and in the week prior to each of the visits at Weeks 2, 8, 16, and 24.

15.1.2 MISSING DATA METHODS FOR PRIMARY EFFICACY VARIABLE

Primary efficacy variable will not be imputed.

15.1.3 ANALYSIS OF PRIMARY EFFICACY VARIABLE

The primary efficacy analysis for the 24-week, double-blind, treatment period will be performed on the Intent-to-Treat (ITT) population, consisting of all patients who were randomized to treatment.

Primary efficacy variable is percent reduction (change) from baseline in the number of apnea episodes (each ≥ 10 seconds in duration) per hour, during awake time, obtained from the BioRadio™.

The primary efficacy test of hypothesis is as below:

H₀: There is no difference in mean percent reduction (change) from baseline in number of apnea episodes in placebo and Sarizotan high dose group.

H_A: There is a difference in the mean percent reduction (change) from baseline in number of apnea episodes in placebo and Sarizotan high dose group..

Document:	\\ieedc-vnasc01\BIOSdata\Newron\Sarizotan\PXA76395\Biostatistics\Documentation\SAP		
Author:	[name]	Version Number:	V2
		Version Date:	[30March2020]
Template No:	CS_TP_BS016 – Revision 4	Reference:	CS_WI_BS005
Effective Date:	01Apr2016		

Descriptive statistics will be presented for actual value, change from baseline and percentage change from baseline in apnea episodes by visit and treatment groups.

Prior to analyzing the primary efficacy data, a blinded data review will be performed to identify outliers. The potential outliers would be examined and determined if the value is clinically plausible and removed from the analysis if not. The primary inferential comparison between treatment groups will be done using a restricted maximum likelihood (REML)-based, mixed-effects repeated measures model approach (MMRM) along with 95% confidence interval for the difference between treatment groups for percent change from baseline in the number of apnea episodes. The MMRM model will include percent change from baseline as response, the fixed, categorical effects of treatment group, visit, treatment group-by-visit interaction, and the continuous terms age and baseline value as covariate. The data collected at Baseline, Week 2, Week 8, Week 16 and Week 24 will be used in the MMRM model.

An unstructured covariance matrix will be used to model the within-subject correlation. The Kenward-Roger approximation will be used to estimate denominator degrees of freedom. If the model for unstructured covariance matrix fails to converge, other covariance structures will be considered using Akaike information criterion/Bayesian information criterion method to find appropriate covariance structure, for e.g. a heterogeneous autoregressive covariance structure.

The differences in LS means will be calculated along with associated standard errors, 2-sided 95% confidence intervals and p-values.

The above analysis will also be repeated on the PP population.

A sensitivity analysis will be performed for the ITT population to include all data (including outliers) to check the robustness of the primary analysis to potential outliers.

Additionally, graphical presentations will be provided.

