15.2.6 Efficacy evaluations

Primary Efficacy Outcome

The primary efficacy outcome will be the percent reduction (change) from baseline in the number of apnea episodes (each ≥ 10 seconds in duration) per hour, during awake time. This will be calculated from the data obtained during home respiratory monitoring by means of an ambulatory data acquisition system (BioRadio™) designed to record specific respiratory and cardiac parameters. Assessment of the respiratory outcomes will be performed at home on any 3 days in each of the first 3 weeks of the Screening period, and in the week prior to each of the visits at Weeks 2, 8, 16, and 24. Monitoring will be performed when the patient is awake and should be attempted for 6 hours on each of the 3 days. Data from all of the quality recording time (minimally 3 hours) in the Screening period, and from the week prior to each of the visits at Weeks 2, 8, 16, and 24, will be averaged and used in calculating the value for the primary efficacy measure. If the patient meets the criterion for number of apnea episodes, as determined by Vivonoetics, in any week of the Screening period, home monitoring in the subsequent week(s) would not be required, and the screening data would be used to calculate the baseline value for the analyses.

The primary efficacy analysis for the initial, 24-week, double-blind, treatment period will be performed on the Intent-to-Treat (ITT) population, consisting of all patients who were randomized to treatment. The percent reduction (change) from baseline in the number of apnea episodes (each ≥ 10 seconds in duration) per hour will be compared between treatment groups using a Mixed Model Repeated Measures (MMRM) analysis. The MMRM model will include percent change from baseline as response, the fixed, categorical effects of treatment group, visit, treatment group-by-visit interaction, and the continuous terms age and baseline value as covariate. A statistically significant difference between high dose sarizotan (5 or 10 mg *bid*) and placebo will be considered evidence of efficacy in reducing apnea.

Key Secondary Efficacy Outcome

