Sample sizes of 23 or 34 in each treatment group would have 90% power to detect a difference in mean percent reduction of -20% or -10%, respectively, assuming a common SD of 20 (for the 20% reduction) and 12.5 (for the 10% reduction), using a two group t-test with a 0.050 two-sided significance level. Assuming an attrition rate of 25% (7 or 9 patients) per group, a total of 30 or 43 patients would need to be enrolled in each group to get 23 or 34 patients completing the study. As this is the first large-scale study evaluating the effect of sarizotan on respiratory symptoms in patients with RTT, a conservative estimate of 10% reduction in apnea episodes was used to estimate the sample size required, i.e. approximately 43 patients per group.

Mode of dose: Oral (capsules), or as a solution either orally (for patients with swallowing difficulties) or through a gastrostomy tube (G-tube)

Blinding:

A randomization number corresponding to the treatment assignment was assigned to each randomized subject using an Interactive Web Response System (IWRS), and was registered in the subject’s files for identification. If it was necessary to break the blind during the double-blind period for reasons of safety, the Investigator was able to break the blind using the IWRS. The Investigator was asked to inform the Sponsor and their representative of this as soon as possible and to provide a reason for the unblinding.

Document:	\\ieedc-vnasc01\BIOSdata\Newron\Sarizotan\PXA76395\Biostatistics\Documentation\SAP		
Author:	[name]	Version Number:	V2
		Version Date:	[30March2020]
Template No:	CS_TP_BS016 – Revision 4	Reference:	CS_WI_BS005
Effective Date:	01Apr2016		

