7.3. MISSING DATA

All data obtained for the ITT population will be used in the analysis. Missing efficacy data for the primary endpoint will not be imputed. Last observation carried forward (LOCF) method will be adopted as imputation for the secondary quantitative endpoints (wherever required). Details of which endpoint will be imputed using LOCF approach can be found in the respective endpoint's section description.

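### The primary MMRM omits a baseline-by-visit term: a small precision loss if the baseline slope changes over visits, and a modest Week 24 bias only if baseline-related dropout also differs by arm

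*SAP*

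**What the plan says.** SAP 15.1.3 specifies a REML mixed model for repeated measures on percent change from baseline. Its mean model contains treatment, visit, "treatment group-by-visit interaction, and the continuous terms age and baseline value as covariate". Protocol 15.2.6 lists the same terms: "the fixed, categorical effects of treatment group, visit, treatment group-by-visit interaction, and the continuous terms age and baseline value as covariate". SAP 7.1 adds no covariate interaction.

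On visits, the SAP says "The data collected at Baseline, Week 2, Week 8, Week 16 and Week 24 will be used in the MMRM model". Percent change is zero by definition at baseline, so I read the model as having four post-baseline visits. I take Week 24 as the primary contrast, following protocol 11.2 and 12.2.1.

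On covariance: "An unstructured covariance matrix will be used to model the within-subject correlation", with Kenward-Roger degrees of freedom. On missing data, SAP 7.3 states "Missing efficacy data for the primary endpoint will not be imputed", and SAP 15.1.2 repeats this. The only dropout figure is in the sample-size text of SAP 3.1: "Assuming an attrition rate of 25% (7 or 9 patients) per group".

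The repeats (per-protocol and outlier-inclusive in SAP 15.1.3, plasma level above 400 ng/mL in SAP 15.2.4) use the same model.

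**The concern.** With nothing imputed, the Week 24 contrast for patients who leave rests on the mean model being right at each visit. A single baseline term assumes that percent change depends on baseline equally strongly at Week 2 and at Week 24.

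There are reasons to doubt that. Patients must show at least 10 apnea episodes per hour to enter. Screening recordings may stop once the criterion is met, and those data become baseline. Baseline is also the denominator of the response. Week 2 is close to screening and Week 24 about six months away. If the correlation with the screening value fades, the slope steepens and the common slope is too shallow at Week 24.

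Two things would then be at stake: some avoidable residual variance at Week 24, and incomplete adjustment if the arms end up with completers of different baseline severity. This contrast is the only element of the success rule in SAP 15.1.4 that must reach significance, since the CIC needs only a favourable direction. None of the planned repeats would reveal the problem, because all keep the single slope.

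**Working it through.** **The plan's own figure.** Inputs from SAP 3.1: difference 10, SD 12.5, two-sided 0.05, power 90%. The normal formula n = 2(1.960 + 1.282)² × (12.5/10)² gives 32.8, so 33. The exact two-sample t calculation gives 33.83, so 34 per group with power 90.15%, as stated. The enrolled 43 is 34 × 1.25 = 42.5, rounded up. (Dividing by 0.75 would give 46. That is a separate matter, and 43 is used below.)

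**Set-up (assumed, since the documents give no slopes).** Three arms, four visits, true contrast -10, total SD 12.5 at each visit, residual AR(1) correlation 0.6, 25% monotone dropout after Week 2. Slopes are per SD of baseline:
- flat: -3.75 throughout (correlation 3.75/12.5 = 0.3);
- moderate: -1.25 to -5 (0.1 to 0.4);
- steep: 0 to -7.5 (0 to 0.6).

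Dropout was unrelated to baseline, related alike in all arms (odds ratio 2 per SD), related in the high-dose arm only (2), or opposite (2 in high dose, 1/2 in placebo). Both models were fitted by maximum likelihood with unstructured covariance; age was left out.

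**Bias.** Error in the Week 24 high-dose minus placebo contrast, 150,000 patients per arm:

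| Slopes | Dropout | Common slope | Visit slopes | Difference |
|---|---|---|---|---|
| Moderate | unrelated | +0.052 | +0.058 | -0.006 |
| Moderate | alike | -0.032 | -0.038 | +0.006 |
| Moderate | high dose only | +0.352 | -0.027 | +0.379 |
| Moderate | opposite | +0.749 | -0.007 | +0.756 |
| Steep | unrelated | +0.133 | +0.130 | +0.003 |
| Steep | alike | +0.049 | +0.038 | +0.011 |
| Steep | high dose only | +0.624 | +0.005 | +0.619 |
| Steep | opposite | +1.193 | -0.012 | +1.205 |

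With flat slopes the difference is at most 0.012 in any pattern. Each estimate has a Monte Carlo SE of about 0.04-0.05. Both models saw the same data, so I read only the last column.

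The mechanism is slope gap times arm imbalance in completers' baseline. Opposite dropout, steep: gap 7.5 - 3.97 = 3.53, and 1.205/3.53 = 0.34 SD. Opposite, moderate: gap 5 - 2.96 = 2.04, and 0.756/2.04 = 0.37 SD. The implied imbalances agree. When dropout acts alike in all arms the imbalance is zero and the error cancels.

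A positive sign here works against sarizotan, because severe high-dose patients leave more often. Reversing the pattern reverses the sign.

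**Precision.** The common slope adds (common slope - Week 24 slope)² to the Week 24 residual variance. With dropout unrelated to baseline:
- moderate: residual variance 12.5² - 5² = 131.25; added (5 - 3.06)² = 3.76; SE ratio √(135.01/131.25) = 1.014;
- steep: 12.5² - 7.5² = 100; added (7.5 - 4.11)² = 11.5; SE ratio √(111.5/100) = 1.056.

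In 600 simulated trials of 43 per arm, mean model SEs (common vs visit-specific) were 2.90 vs 2.90 flat, 2.84 vs 2.80 moderate (ratio 1.014) and 2.58 vs 2.43 steep (1.062).

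**Bias in standard errors.** Opposite dropout: 0.756/2.85 = 0.27 (moderate) and 1.205/2.60 = 0.46 (steep). By normal approximation, a nominal two-sided 5% test becomes Φ(-1.69) + Φ(-2.23) = 5.8% and Φ(-1.50) + Φ(-2.42) = 7.5%.

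**The case against.** Much of the case against this point stands.

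- A reader might infer that the slope must strengthen with time. The documents do not show it. If each patient has a stable level plus measurement error, regression to the mean is complete by Week 2 and the slope is flat.
- A reader might also infer that any baseline-related dropout biases the result. It does not. Acting alike in all arms, it produced about 0.01 points.
- Nothing in the documents predicts arm-differential dropout. They give one overall attrition figure. The SAP introduction reports that emerging data showed no intolerance, dose reduction is allowed, and open-label sarizotan requires completing Week 24, which gives placebo families a reason to stay. Leaving for lack of effect would depend largely on observed response, which the MMRM already uses.
- With complete randomised data, the common slope causes no bias.

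These arguments make the bias less likely without excluding it. A visit value also needs at least 3 hours of quality recording, so data can be missing without discontinuation, and nothing shows that such losses are balanced by baseline across arms. The precision argument needs only changing slopes, not differential dropout.

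**Conclusion.** The omission is real and the consequences are conditional and small. If the slope changes over visits, the Week 24 SE is about 1-6% larger than it need be. If baseline-related dropout also differs by arm, the bias is about 0.4-0.6 points (one arm only) or 0.8-1.2 points (opposite directions) at SD 12.5, in either direction and under half an SE. With correlations held fixed, the bias in points scales with the SD but the ratio to the SE does not change.

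A larger spurious effect might be inferred. A log-normal simulation with no true difference and arm-differential dropout gave 0.5-3.3 points in favour of sarizotan, but with Week 24 SDs of 18-44, so the upper end should not be set against a 10-point effect planned at SD 12.5.

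All slopes, correlations and odds ratios are assumptions, and maximum likelihood stood in for REML with Kenward-Roger. This is a near-free improvement to an otherwise sound model. It is not evidence that the primary test is invalid.

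**What to change.** Before unblinding, add a baseline-by-visit interaction to the MMRM in SAP 15.1.3 and protocol 15.2.6. Keep the unstructured covariance and Kenward-Roger. Use the same model in the per-protocol, outlier-inclusive and above-400 ng/mL repeats. If the protocol text is not changed in step, record the difference in SAP 3.3, which now reports no changes from the protocol.

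The cost is three parameters (four slopes in place of one), one line of text and code, and no new data. With flat slopes the simulated SEs were equal or at most 0.02 larger (2.95 vs 2.93), and the empirical variance ratio (common over visit-specific) was 0.98-0.99. Age-by-visit is optional: age was not in the simulations, so nothing here shows that it matters.

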15.1.4 KEY SECONDARY EFFICACY VARIABLE

The key secondary efficacy outcome was the difference between sarizotan and placebo on the Caregiver-rated Impression of Change (CIC) from baseline, a 7-point Likert-type scale for which ratings range from 1 = very much improved to 7 = very much worse, with 4 = no change. The key secondary efficacy analysis will be performed for the ITT population.

Summary statistics for CIC mean rating scores will be provided by visit and treatment group.

The mean rating of the caregiver-rated CIC at Week 24 LOCF will be compared between treatment groups using the Van Elteren test (a stratified Cochran Mantel Haenszel test with modified ridit scores). The following age strata will be considered in the analysis:

<13 years

>=13 years

Improvement on the CIC (i.e. Responder) will be defined as a Likert scale score of 1 (very

Document:	\\ieedc-vnasc01\BIOSdata\Newron\Sarizotan\PXA76395\Biostatistics\Documentation\SAP	Version Number:	V2
Author:	[name]	Version Date:	[30March2020]

Template No: CS_TP_BS016 – Revision 4
 Effective Date: 01Apr2016

Reference: CS_WI_BS005

much improved), 2 (much improved) or 3 (minimally improved). The proportion of patients with a rating of improvement in the CIC (n, count, and percent) will be presented at post-baseline visits by treatment group.

In addition to the above analysis, comparisons between treatments for the proportion of responders at Week 24 LOCF will be done using logistic regression. The logistic regression model will include treatment group and age. For the treatment comparison, an estimate of the odds ratio, corresponding Wald 95% CI and chi-square p-value will be presented.

Additionally, graphical presentation will be provided for the proportion of responders at Week 24.

In accordance with the original protocol (dated 27 October 2015, Section, page 70, Section 15.2.6) and the amended protocol (version 11.0, incorporating protocol Amendment 10, dated 29 November 2018, page 100, Section 15.2.6) as referred to in the FDA minutes of the meeting of February 5, 2020 issued by the FDA March 4, 2020, the Sponsor has reverted to using the “win” criteria referred to in these sections, as directed by FDA. A statistical “Win” will be claimed if the following results are obtained in the primary and key secondary efficacy analyses:

- Statistically significant difference between high dose sarizotan (5 or 10 mg bid) and placebo in the percent reduction (change) from baseline in the number of apnea episodes (each ≥ 10 seconds in duration) per hour, during awake time;
- Directional change on the CIC in favor of high dose sarizotan (5 or 10 mg bid) group compared to placebo.

